5.1.2 Pre-Treatment Evaluation (Evaluation Table Appendix 1)

These must be obtained within 30 days of enrollment.

1. Complete history and physical examination (including a skin exam)
2. Karnofsky functional status

3. Complete neurological examination including visual acuity when possible
4. Laboratory assessment:
 - a. Complete blood count
 - b. Renal function studies (BUN, creatinine)
 - c. Hepatic function studies (ALT, AST, T bilirubin, alkaline phosphatase)
 - d. Endocrine function studies (TSH, Free T4, IGF-1, IGF-BP3, cortisol) as clinically warranted
5. MRI scan of the brain
6. MRI scan of the spine, only if clinically warranted

5.1.3 Preoperative Administration of Photofrin®

The subjects entering the study will receive a prescribed dose of 2.5 mg kg^{-1} of Photofrin® (supplied by Pinnacle Biologics, Inc., Bannockburn, IL), given intravenously over 3-5 minutes during an outpatient clinic visit, scheduled 24 hours prior to the planned surgical resection. Research participants will report to the Adult Translational Research Unit (TRU) to receive the injection by a TRU nurse. Prior to the administration of Photofrin® the TRU nurse will assess the patient and ensure the patient has adequate protective gear and clothing for the patient's journey home and back to the hospital for tumor resection the following day. Subjects will have already received a PDT Patient Kit and instructions for protection from sunlight. Subjects will be advised to remain out of direct sunlight and bright artificial lighting for at least 30 days and up to 90 days after Photofrin® injection and PDT. (Appendix 2) If a photosensitivity reaction occurs, subjects are instructed to contact their physician immediately for guidance in the treatment of the reaction.

5.1.4 Surgical Treatment for Tumors – Craniotomy and Resection

Craniotomy and tumor resection will be carried out in the standard fashion in order to achieve the maximum tumor resection compatible with preservation of neurological function.

5.1.5 Operative Treatment and Intraoperative PDT of the Tumor

After tumor resection, room temperature Intralipid (Fresenius Kabi) will be infused into the open craniotomy and maintained for approximately 45-90 minutes, while PDT will be performed. The rational for the time frame listed includes the time it would take to drape the photosensitive patient, calibrate the optical fiber(s) verify the dose calculations, place the optical fibers in the tumor cavity, administer PDT laser light dose of 240 J cm^{-2} , and remove the optical fiber(s). All efforts will be made to minimize additional time in the OR. Up to a combination of 2 lasers may be used to supply the prescribed light dose of 240 J cm^{-2} .

The Intralipid will diffuse the light and ensure uniformity of light delivery, and will be replenished as needed at the discretion of the surgeon. The temperature of the tumor cavity can

be monitored by use of the Licox probe and should be maintained at normal body temperature (37°C).

Photoactivation of Photofrin® is controlled by the total light dose delivered over the treatment time. PDT lasers are equipped with a calibration unit to calibrate the fibers and yield the required power density output (mW) necessary to deliver a light dose of 240 J cm⁻². The illumination time will be calculated from the power density (mW) emitted by the laser through the fiber, and the radius (r) of the resection cavity to deliver a total light dose (energy) of 240 J cm⁻² at a wavelength of 630 ± 3 nm using the following formula:

$$\text{Treatment Time (sec)} = \frac{\text{Light Dose (J cm}^{-2}\text{)} \times \text{Cavity Surface (cm}^2\text{)} \times 1000}{\text{Power Density (mW)}}$$

$$\text{Where, Cavity Surface (cm}^2\text{)} = 4 \cdot \pi \cdot r^2$$

The optic fiber or fibers output will be calibrated to the appropriate power density setting using the FDA approved laser calibration unit or units according to the procedure described in the laser manufacturer's instructions, or using a suitable external calibration unit.

The subject's head will be positioned on the operating table such that the tumor resection cavity is uppermost. The optical fiber will be placed in the approximate center of the surgical cavity and photoillumination will commence. The laser light exposure time will be calculated as above. An optic fiber probe may be used at the time of photoillumination to measure the light flux in the brain or brain tumor in order to ensure that no fall off of light penetration into the cavity surface occurs during treatment.

After PDT, the intralipid solution will be removed and the wound will be closed. The subject will be extubated, recovered from anesthesia, and then sent to the intensive care area for appropriate observation.

5.1.6 Acute Postoperative Care

1. When clinically indicated, subjects will be monitored in the Neurosurgical Intensive Care Unit for approximately 72 hours postoperatively or as long as deemed clinically appropriate by the care team.
2. When clinically indicated, subjects will have continuous intracranial pressure monitoring for approximately 48 postoperative hours or as long as deemed clinically appropriate.
3. When clinically indicated, subjects will receive postoperative dexamethasone at a dose

and for a time period dictated by their clinical condition. The dose and duration steroid administration will be recorded.

4. Subjects will receive anticonvulsants as deemed clinically appropriate.
5. Subjects will get an MRI of the resection site 1–3 days following PDT to assess the degree of resection
6. Subjects will receive any additional laboratory and imaging evaluations as clinically indicated.
7. Subjects will continue to be reminded and educated regarding PDT, the precautions in place to prevent phototoxicities by minimizing exposure to intense light and avoiding other phototoxic medications.

5.1.7 Follow-Up

- **Required Standard of Care MRI Evaluations:** Patients will have a post-operative MRI of brain on Day +2 (\pm 1 day), 1st-Month/Week +4 (\pm 3 days)follow-up, and 6-Month/Week +24 follow-up with and without gadolinium pending scan results, patient's clinical exam and healing of incision site.
- **First Month:** Patient will be followed in the neurosciences clinic at Froedtert Health-MCW Cancer Care Center for a minimum of once a week for four weeks following PDT as part of their postoperative standard of care for brain tumor resection. During these clinic visits, patients will have a history and physical exam including thorough neurological exam and documentation of medicines and doses administered. Interval history and physical exams will focus on identifying toxicities related to Photofrin® or the PDT procedure. Additional laboratory and imaging studies will be performed as clinically indicated.
- **After the First Month:** Many study participants will go on to receive additional anti-cancer therapy following recovery of neurosurgery during this time. Therapy dosing and schedule will also be recorded for study purposes as outlined in this protocol. Patients will be followed at a schedule to be determined by their respective treating physicians. For study purposes and as part of their routine care, patients will be evaluated from Week +1 to Year +3, as clinically indicated, without study specific follow-up time points. During this time, the study coordinator will report survival status when required for DSMC review, study progress reports, as well as FDA and IRB annual reports. This is outlined in Appendix 1. Evaluation will include a thorough history and physical, MRI of the resection area, medications and doses and laboratory evaluations deemed clinically appropriate.

5.2 Concomitant Therapy Restrictions

5.2.1 Concomitant Medications

Subjects should not receive other photosensitizing drugs while on protocol therapy or in toxicity review. Appendix 3 lists the commonly prescribed drugs that are known photosensitizers. Subjects must use precaution if receiving potentially photosensitizing drugs for the first three months following administration of Photofrin®. The patient and family will be instructed to call the Phase II team prior to starting any new medications in the first three months (until Week + 13, of Day + 90) after Photofrin® administration.

5.2.2 Post PDT Anticancer Therapy

Many of these patients will receive additional therapy for their recurrent cancer. Therapy dosing and schedule must be recorded for study purposes. Patients may begin other anticancer therapy regimens as early 1 month after PDT. Anticancer therapy starting before 3 months (90 days) after PDT should proceed with caution if the regimen contains any possible phototoxic agents.

5.3 Modifications For Toxicities

There will be no dose modifications for the administration of Photofrin®. All enrolled patients will receive 2.5 mg kg⁻¹. If the enrolled patient does not receive the full investigation drug dose or complete the intraoperative photodynamic therapy for any reason, the patient should be evaluated for toxicities for 90 days. The patient must follow the precautions and consideration of Photofrin® risks.

6.0 SUPPORTIVE CARE GUIDELINES AND OTHER CONCOMITANT THERAPY

6.1 Standard Surgical Risks

Supportive care and treatment for reported operative and postoperative adverse events associated with standard care craniotomy and resection will be given as appropriate to each patient (anti-emetics, antibiotics, transfusions, oxygen therapy, nutritional support, palliative treatment for pain etc.) according to institutional guidelines.

- A. General postoperative complications**
 - 1. Reversal agents for anesthetic complications—as needed if a preoperative level of consciousness is not obtained
 - 2. Respiratory complications
 - a. Decreased level of consciousness and inability to protect airway following surgery
 - b. Development of edema in and around the brain stem
 - 3. Cardiovascular complications
 - a. Hypovolemic shock
 - b. Blood pressure—usually normotensive state is maintained
 - c. Cardiac arrhythmias
 - 4. Gastrointestinal complications—gastric stress ulceration and hemorrhage
 - 5. Endocrine complications
 - a. Diabetes insipidus
 - b. Syndrome of inappropriate antidiuretic hormone (SIADH)
 - c. Cerebral salt wasting
 - 6. Infectious complications
 - a. Meningitis
 - b. Brain abscess
 - c. Intracranial epidural abscesses
 - 7. Hematological complications
 - a. Deep vein thrombosis (DVT)
 - 8. Pain
- B. Specific neurologic complications**
 - 1. Hemorrhage
 - 2. Increased intracranial pressure
 - 3. Peritumoral edema
 - 4. Cerebral infarction

5. Pneumocephalus
6. Hydrocephalus
7. Seizures
8. Cerebrospinal fluid leak
9. Cranial nerve deficits
10. Wound infection

6.2 Supportive Care for Intraoperative PDT Risks

Increased surgical risk due to the PDT procedure is expected to be minimal, as the subject will be undergoing a standard care tumor resection.

6.2.1 Photoillumination of the Tumor Resection Cavity

The addition of an illumination stage results in minor additional risk limited to increased temperature due to light energy. An Intralipid bath will be utilized to control for this possibility. Intralipid has micron-sized lipid droplets that efficiently scatter the light. By placing the distal end of the laser fiberoptic directly in this lipid droplet suspension the 630 nm laser light is evenly distributed within the tumor resection cavity, thus activating Photofrin® evenly over the entire exposed tumor inner surface area. This reduces risk of any areas of over- or under-exposure to light, controlling the photodynamic effect, and avoiding "spotty" overdose or under-dose.

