2.6 Relevant Clinical Data

2.6.1 Photoillumination and Postoperative Intracranial Pressure

Muller and Wilson have reported that using photoillumination of the tumor cavity had increased intracranial pressure in the immediate postoperative period, but this was easily controlled with steroid therapy.^{16,19} The PS used was either HpD or DHE, and fluences were 8-175 J cm⁻¹. As patients will typically be on steroid therapy, we do not anticipate problems with increased intracranial pressure; we will be paying special attention however to any increased steroid requirements. Muller also reported on 50 cases of malignant glioma treated with cavitary photoillumination and suggested that greater light doses resulted in increased survival.¹⁶

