2.6.3 Styli and Kaye *et. al.*: PDT 3 Year Survival Analysis

Clinical studies by Styli and Kaye *et al.*⁴ report on hematoporphyrin derivative (HpD) mediated-PDT that had been investigated as an adjuvant treatment for cerebral high-grade glioma. The study recorded the survival of patients at the Royal Melbourne Hospital, utilizing the Victorian Cancer Registry database for patients treated with adjuvant PDT following surgical resection of the tumor. For primary (newly diagnosed) tumors, median survival from initial diagnosis was 76.5 months for anaplastic astrocytoma (AA) and 14.3 months for glioblastoma multiforme (GBM). 73% of patients with AA and 25% with GBM survived longer than 36 months. For recurrent tumors, median survival from the time of surgery was 66.6 months for AA and 13.5 months for GBM. 57% of patients with recurrent AA and 37% of patients with recurrent GBM survived longer than 36 months. Younger patients (< 40) had even better survival. These survival data for high-grade glioma patients are superior to the current published survival rates in adult as well as pediatric studies. Laser light doses above the sample median of 230 J cm⁻² were associated with better prognosis in the 136 patients studied. There was no mortality directly associated with the therapy; three

patients had increased cerebral edema thought to be related to PDT that was controlled with conventional therapies. No patients had permanent neurological deficit. Of the 29 patients who received chemotherapy, no association between the use of chemotherapy and prognosis following PDT was found.

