6.4 Overall Adverse Reaction Profile

Systemically induced effects of photodynamic therapy (PDT) with Photofrin® consist of photosensitivity and mild constipation. All patients who receive Photofrin® will be photosensitive and must observe precautions to avoid sunlight and bright indoor light. Photosensitivity reactions occurred in approximately 20% of cancer patients and in 69% of high-grade dysplasia (HGD) in Barrett's esophagus (BE) patients treated with Photofrin®. Typically these reactions were mostly mild to moderate erythema but they also included swelling, pruritus, burning sensation, feeling hot, or blisters. In a single study of 24 healthy subjects, some evidence of photosensitivity reactions occurred in all subjects. Other less common skin manifestations were also reported in areas where photosensitivity reactions had occurred, such as increased hair growth, skin discoloration, skin nodule, skin wrinkling and increased skin fragility. These manifestations may be attributable to a pseudoporphyrin state (temporary drug-induced cutaneous porphyria).

In the Australian study conducted in 136 adult patients, there were no direct serious complications from the PDT itself. One patient died from acute myocardial infarction and another suffered a hemiplegia (total paralysis of the arm, leg, and trunk on the same side of the

body) after tumor resection. Three patients had increasing drowsiness (somnolence) and hemiparesis (muscle weakness on only one side of the body) associated with cerebral edema (excess accumulation of water in the brain) despite usual doses of steroid. All three cases resolved after the use of steroids and diuretics.

In the US pediatric and adult study, two out 20 patients developed complications. Immediately postoperatively, one patient developed severe truncal ataxia (lack of muscle coordination), bilateral facial weakness as well as dysphagia (difficulty swallowing). The other patient who underwent an extensive reoperation followed by laser light PDT, had a right facial nerve palsy (paralysis), which improved in 3 months, but did not completely resolve.

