12.4 Reporting Methods for SAEs

Steps to Determine if an Adverse Event Related to DRUG or the Regimen as a Whole is to be Reported in an Expedited Manner

Step 1: Identify the event type using the NCI Common Toxicity Criteria (CTC), version 4.0.

The CTC provides descriptive terminology and a grading scale for each adverse event listed. A copy of the CTC can be downloaded from the CTEP home page (<http://ctep.cancer.gov>). Additionally, if assistance is needed, the NCI has an Index to the CTC that provides help for classifying and locating terms. All appropriate treatment locations should have access to a copy of the CTC.

Step 2: Grade the event using the NCI CTCAE.

This study will utilize version 4.0 of the CTCAE of the National Cancer Institute (NCI) for toxicity and performance reporting. A copy of the CTCAE version 4.0 can be downloaded from the CTEP website. Additionally, toxicities are to be reported on the appropriate case report forms.

Step 3: Determine whether the adverse event is related to the protocol therapy.

The investigator will assess the causal relationship between the investigational product and the adverse event. The investigator will use his/her clinical expertise and judgment to select the attribution category below that best fits the circumstances of the AE.

Attribution Categories:

❖Unrelated❖	❖Unlikely❖	❖Possible❖	❖Probable❖	❖Definite❖
-------------	------------	------------	------------	------------

Unrelated:

- The adverse event is clearly unrelated to the investigational agent(s).
- Does not follow a known response pattern to the suspect investigational product (if response pattern is previously known)
- Can be explained by the known characteristics of the patient's clinical state or therapy administered to the patient

Unlikely:

- a. The adverse event is doubtfully related to the investigational agent(s).
- b. May or may not follow a reasonable temporal sequence from administration of the investigational product.
- c. Likely explained by the known characteristics of the patient's clinical state

or other therapy administered to the patient

Possibly Related:

- a. The adverse event may be related to the investigational agent(s).
- b. Follows a reasonable temporal sequence from administration of the investigational product
- c. May also be reasonably explained by the patient's clinical state or therapy administered to the patient.

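### Section 6.2.1 limits the added risk of illumination to heat, although the protocol's background attributes cerebral edema and raised intracranial pressure to PDT; this can steer attribution and lower the stopping count

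*Combined protocol and SAP*

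**What the plan says.** **Risk sections.** Section 6.2 opens with "Increased surgical risk due to the PDT procedure is expected to be minimal", and 6.2.1 then says "The addition of an illumination stage results in minor additional risk limited to increased temperature due to light energy". Section 6.1 covers "operative and postoperative adverse events associated with standard care craniotomy and resection", and its neurologic list includes raised intracranial pressure and peritumoral edema. Neither 6.2 nor 6.3 names these two events as risks of PDT or of Photofrin.

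**Background.** Section 2.4 gives cerebral edema, next to skin photosensitization, as an example of a PDT complication. Section 2.6.1 cites reports that "using photoillumination of the tumor cavity had increased intracranial pressure in the immediate postoperative period". Section 2.6.3 says of the 136-patient Australian series that three "patients had increased cerebral edema thought to be related to PDT".

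**Section 6.4.** The same series is described as free of direct serious complications of PDT. The section then lists three patients with drowsiness and hemiparesis "associated with cerebral edema (excess accumulation of water in the brain) despite usual doses of steroid".

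**Stopping count.** The table in 13.3.4 counts patients with an SAE attributed to the protocol. Section 13.3.3 speaks of SAEs related to Photofrin and leaves that judgment to the PI. Section 13.3.2 accepts possible attribution to the drug, device or therapy. Its fourth category takes any other toxicity of Grade 4 or higher. Its neurotoxicity item covers deficits that persist at 4 weeks.

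**The concern.** An investigator who consults Section 6 to judge a case of postoperative edema finds edema listed under surgery and the illumination risk confined to heat. The evidence that PDT may itself cause edema or raised pressure lies in Section 2, and 6.4 presents the same cases without attributing them to PDT. In 12.4, attribution turns partly on whether an event fits a known response pattern and whether something else explains it. An incomplete statement of the known pattern therefore bears on that judgment.

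What is at stake is the only numeric safety trigger in a single-arm trial that has no concurrent control to show an excess of edema. Section 13.3.2 concedes that separating resection from PDT will be difficult. The localization work it plans is set out for the neurotoxicity item, which concerns deficits persisting at 4 weeks. Acute edema or pressure has no attribution guidance of its own.

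**Working it through.** **1. The passages side by side.**

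| Section | Edema or raised pressure |
|---|---|
| 6.1 | Listed under standard craniotomy and resection |
| 6.2.1 | Not mentioned; added risk confined to heat |
| 2.4 | Cerebral edema is a PDT complication |
| 2.6.1 | Raised pressure follows cavity photoillumination |
| 2.6.3 | Three edema cases thought to be PDT-related |
| 6.4 | Same three cases, but no direct serious PDT complication |

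Section 6.2.1 cannot stand with 2.4, 2.6.1 and 2.6.3. Section 6.4 conflicts with 2.6.3 on the same patients.

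**2. The attribution standards.** Section 13.3.2 asks for possible attribution to drug, device or therapy. Section 13.3.3 asks for a relation to Photofrin, judged by the PI. The footnote in 13.3.4 asks for attribution to the protocol. These are three wordings for one count.

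**3. Rate in the cited series.** 3/136 = 0.0221, or 2.2%. Expected cases in 30 patients: 30 × 0.0221 = 0.66. Chance of at least one: 1 − (1 − 3/136)^30 = 0.49. This concerns any such case, not necessarily one that would count.

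**4. Effect on the boundary.** The documents give no threshold rate and no operating characteristics for the 13.3.4 table, so there is no stated figure to reproduce. The boundary x(n) is 2 for n = 1-6, 3 for 7-12, 4 for 13-18 and 5 for 19-30. I assume that it is checked after each patient. With per-patient probability p of a counted SAE, let P_n(k) be the probability of k counted patients after n with no trigger so far:

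P_n(k) = (1 − p)·P_{n−1}(k) + p·P_{n−1}(k − 1)

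At each n, the probability at k ≥ x(n) is removed. The removed amounts, summed to n = 30, give the chance of a trigger.

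Let b be the rate of other attributed SAEs and e the rate of qualifying edema or pressure events, taken as independent. With those events left out, p = b. With them counted, p = 1 − (1 − b)(1 − e). At e = 3/136:

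- b = 5%: p = 1 − 0.95 × 0.9779 = 0.071
- b = 10%: p = 1 − 0.90 × 0.9779 = 0.120
- b = 15%: p = 1 − 0.85 × 0.9779 = 0.169

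Chance of reaching the boundary (the 5% and 10% columns are assumed rates, to show the range):

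| Other SAEs (b) | Left out | Counted, e = 2.2% | e = 5% | e = 10% |
|---|---|---|---|---|
| 0% | 0.0% | 0.8% | 5.3% | 26.2% |
| 5% | 5.3% | 12.1% | 24.8% | 52.8% |
| 10% | 26.2% | 37.8% | 52.8% | 75.4% |
| 15% | 55.7% | 65.8% | 76.4% | 89.4% |

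Loss at 2.2%: 12.1 − 5.3 = 6.8 points, 37.8 − 26.2 = 11.6 points, 65.8 − 55.7 = 10.1 points, and 0.8 points when there are no other SAEs.

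**The case against.** The strongest reply is that the plan already counts these events. In 12.4 the unrelated category is for events clearly unrelated to the agent, and the possible category expressly admits events that another therapy could also explain. Edema that could come from surgery or from PDT fits the possible category, and 13.3.2 needs no more than that. Section 6.1 is a supportive-care list. It does not call its entries exclusively surgical, and neither 12.4 nor 13.3 refers to it or to 6.2.1. A careful investigator who has read Section 2 would also know that edema after PDT is a recorded pattern.

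This stands as far as it goes. A reader might infer that PDT edema drops out of the count, or that the count is biased downward. The documents do not support either: no text excludes the events, and the loss arises only if the PI judges a qualifying event to be surgical.

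Other safeguards are real but partial. Section 2.6.1 promises attention to increased steroid requirements, and 5.1.6 has steroid dose and duration recorded, but neither feeds the count. The semiannual reports in 13.3.1 carry all SAE reports whatever their attribution, so the DSMC would see the events, though not through the trigger.

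The size is also open to challenge. The cited cases are ungraded, responded to treatment and left no permanent deficit; under the fourth category of 13.3.2 only Grade 4 or higher would count. A reader might reach a much larger loss by supposing a 15% related-SAE rate with one third assigned to surgery, which takes the trigger chance from 55.7% to 26.2%. The documents give neither figure, and together they imply a 5% rate of such events, more than twice 2.2%.

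Finally, edema and pressure are not the only intracranial harm reported after PDT. The 20-patient pilot described before 2.6.5 includes a significant neurological deficit after interstitial fiber illumination.

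**Conclusion.** The contradiction is established by the text: 6.1, 6.2.1 and 6.4 need to be reconciled with 2.4, 2.6.1 and 2.6.3. The consequence is a possibility, not a rule. Because the PI decides relatedness and the attribution wording varies across 13.3.2 to 13.3.4, the narrow risk statement can move qualifying edema or pressure events to surgery and so delay DSMC consultation.

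Its size is about 7 to 12 percentage points of trigger probability when other attributed SAEs run at 5-15%, and under 1 point when there are none. This assumes that the 2.2% rate carries over, that every such event meets the grade and time rules, that every one is left out, that these events are independent of other SAEs, and that the boundary is checked after each patient. If only some cases qualified or were misattributed, the loss at that rate would be smaller; a higher rate of qualifying events would make it larger. The point warrants a wording amendment and does not affect the efficacy analysis.

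**What to change.** - **Sections 6.1, 6.2, 6.2.1 and 6.4:** remove the restriction of illumination risk to temperature. Name cerebral edema and raised intracranial pressure as risks shared by surgery and PDT, with references to 2.4, 2.6.1 and 2.6.3. Reconcile the account of the 136-patient series in 6.4 with that in 2.6.3.
- **Sections 13.3.2 to 13.3.4:** use one attribution standard throughout, namely at least possible, to drug, device or therapy. Align the narrower Photofrin-only, PI-determined wording of 13.3.3 with it.
- **Default for the count:** state that edema or pressure events meeting the existing grade and time rules count as at least possible unless clearly unrelated to PDT.

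The cost is a text amendment with no change to treatment, sample size or data collection. The downside is that some surgery-caused events may be counted. That is tolerable because, under 13.3.3, reaching the boundary prompts DSMC consultation and does not close enrollment automatically.
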